8.9.4. Efficacy Analyses

8.9.4.1. Primary Analysis

8.9.5. Safety Analyses

8.9.5.1. Adverse Events

Adverse events will be classified by system organ class (SOC) and preferred term (PT) according to the most recent version of MedDRA dictionary.

8.9.5.3. Vital signs

8.9.5.4.
Physical Examination

8.9.5.5.
ECG

9. SAFETY REPORTING

The Investigator is responsible for the detection and documentation of events meeting the criteria and definition of an AE or SAE, as provided in this protocol. During the study when there is a safety evaluation, the Investigator or site staff will be responsible for detecting, documenting, and reporting AEs and SAEs as detailed in this Section of the protocol.

9.1. ADVERSE EVENT (AE) DEFINITION

An adverse event (AE) is defined as any unfavorable or unintended sign, symptom, or disease that occurs or is reported by the patient to have occurred, or a worsening of a pre-existing condition. An adverse event may or may not be related to the study treatment.

AEs will be elicited through direct questioning and subject reports. Any abnormality in physical examination findings or laboratory results that the investigator believes is clinically significant (CS) to the research subject and that occurred after initiation of the first study treatment will be reported as AEs. Abnormal findings that are NOT clinically significant should not be recorded as an AE.

9.2. **REPORTING OF ADVERSE EVENTS**

Report initiation for all AEs and SAEs will begin at the time of the first treatment visit and continue until the end of final study visit. All events will be followed to resolution or until the subject completes the study. A final assessment of outcome will be made at that time.

All AEs must be recorded in the subject's medical records and on the CRF. AEs will be reported using customary medical terminology along with the following information: the onset and end dates, whether the event is considered to be an SAE (see Section 9.3), the impact the event had on study treatment (see Section 9.2.1), the Common Terminology Criteria for Adverse Events (CTCAE) grade (intensity) of the event (see Section 9.2.2), the causality of the event (see Section 9.2.3), whether treatment was given as a result of the event (see Section 9.2.4), and the outcome of the event (see Section 9.2.5)

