4. STUDY SCHEDULE

The study Schedule of Assessments is presented in Table 4-1 and Table 4-2.

The study will have three phases: Screening Phase, Treatment Phase, and Follow-Up Phase.

Note: During visits conducted at the study clinic, subjects and site personnel will use appropriate protective gear (e.g., masks, gloves) to prevent the spread of the infection.

Screening Phase (up to 1 week):

All subjects will provide written informed consent and have a Screening visit (V1) within 7 days prior to first treatment visit (V2) to determine eligibility for subject participation.

All subjects who fail to meet eligibility criteria are considered screen failures and are exited from the study without further evaluation.

Treatment Phase (12 weeks):

Ampligen[®] and placebo will be administered via twice weekly infusions (Example: Monday/Thursday or Tuesday/Friday schedule) for 12 weeks.

Follow-Up Phase (2 weeks):

Two safety follow-up visits will be performed 3 to 4 days and 2 weeks after the End of Treatment (EOT) visit (V25).

Procedure/Assessments	Screening Visit						Treatn	ient Vi	sits					
Visit	V1	V2	V3	V4	V5	V6	V 7	V8	V9	V10	V11	V12	V13	V14
Week	Week 0	1(Day 0)	1	2	2	3	3	4	4	5	5	6	6	7
Window Period		Within 7 days of SV												
	Х													
	Х	Х												
	Х													
	Х	Х												
	Х	Х	Х	X	Х	Х	Х	Х	Х	Х	Х	Х	X	X
	Х	Х	Х	X	X	Х	X	Х	Х	Х	Х	Х	X	Х
	Х	Х										Х		
	Х	Х										Х		
	Х	Х		X		Х		Х		Х		Х		X
		х		Х		Х		х		Х		х		х
		х		Х		х		х		х		х		x
		Х	х	Х	Х	Х	Х	х	Х	Х	Х	х	Х	х
		Х	х		Х		х		х		Х		Х	
	Х	Х		Х		Х		Х		Х		Х		Х
		Х						Х						
	Х					Х						Х		
	Х	Х	Х	Х	Х	Х	Х	Х	Х	Х	Х	Х	Х	Х
		Х	Х	Х	Х	Х	Х	Х	Х	Х	Х	Х	Х	Х
		Х	Х	Х	Х	Х	Х	Х	Х	Х	Х	Х	Х	Х
	х													
	X	Х										Х		
Bio	Х	Х										Х		
	Х	Х						Х	Х					
	Х	X										Х		

Table 4-1:Schedule of Assessments V1 to V14

CONFIDENTIAL

xx x
Image: Constraint of the state of the st

Screening Visit

V1

Week 0

V2

1(Day 0)

V3

1

V4

2

V5

2

V6

3

Procedure/Assessments

Visit

Week

6

V14

7

V11 V12 V13

6

Treatment Visits

V8

4

V9

4

V10

5

5

V7

3

 Table 4-2:
 Schedule of Assessments V15 to V27

Procedure/Assessments		Treatment Visits											Follow-up 2
Visit	V15	V16	V1 7	V18	V19	V20	V21	V22	V23	V24	V25	Visit 26	Visit 27
Week	7	8	8	9	9	10	10	11	11	12	12	Week 13 (3 to 4 days after EOT)	Week 14
Window Period													± 3 days
	Х	Х	Х	Х	Х	Х	Х	Х	Х	Х	Х	Х	Х
	Х	Х	Х	Х	Х	Х	Х	Х	Х	Х	Х	Х	Х
										Х			Х
										Х			X

V25	Visit 26	Visit 27
	Follow-up 1	Follow-up
	Date: 2	3-Aug-2023

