4.1.1. Screening Visit (V1)

Screening assessments will commence at Visit 1 (V1) after obtaining signed informed consent, and will include:

All subjects who fail to meet eligibility criteria are considered screen failures and are exited from the study without further evaluation.

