4.2. TREATMENT PHASE

4.2.1. Randomization (V2)

Visit 2 (Day 0) defined as day of first Ampligen[®] or placebo administration.

Subjects who meet the eligibility criteria will have completed the following evaluations and assessments at V2:

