7.4. MEDICAL HISTORY

A medical history will be recorded during the Screening Phase and will include:

- All ongoing medical conditions
- All previously resolved medical conditions that are relevant in the judgment of the Investigator
- Any prior medical conditions that have resolved within the last year

Events that emerge prior to first dose of study medication on Day 1 will be recorded in the medical history and not as AEs. Aside from being used to determine subject eligibility, this information will permit the Investigator to record the nature, duration, and severity of any ongoing baseline medical conditions prior to the subject's receiving investigational product treatment.

For each relevant history, the following will be documented:

- Disease/disorder/condition
- Date of diagnosis
- History status (resolved or ongoing).

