7.6. VITAL SIGNS, HEIGHT AND WEIGHT

The following will be collected:

- Systolic Blood Pressure
- Diastolic Blood Pressure
- Heart Rate (Pulse)
- Temperature
- Respiratory Rate
- Height (Screening only)
- Weight
- Body Mass Index

Note: During days of Ampligen® or Placebo administration, pre-infusion vitals (before the start of infusion) and post-infusion vitals (after the end of infusion) will be measured. Post-infusion vitals will be limited to blood pressure and pulse only.

Note: During study visits when the 6MWT is performed, vitals should be collected before and after 6MWT (i.e., pre 6MWT, and post 6MWT), as clinically indicated per the discretion of the Investigator or designee. These should be documented in the source records as standard of care assessments; however, they will not be captured as a protocol assessment.

Note: During study visits when the 6MWT and study drug administration is performed (i.e., Visit 6, 12, and 18), vitals should be collected as follows: pre 6MWT and post 6MWT, if clinically indicated per the discretion of the Investigator or designee. Subjects should be rested

for at least 10 minutes after completing the 6MWT before pre-infusion vitals are taken. Postinfusion vitals should be taken after the completion of the study administration.

7.7. **30** MINUTE SITE CHECK

Subjects will be monitored for 30 minutes after every infusion for evaluation of any unexpected adverse events.

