9.3. SERIOUS ADVERSE EVENT (SAE) DEFINITION

An SAE is defined as any AE that:

- Results in death
- Is life threatening (the subject is at immediate risk of dying from the adverse experience)
- Requires subject hospitalization or prolongs existing hospitalization
- Results in persistent or significant disability/incapacity
- Is a congenital anomaly/birth defect
- Important medical events that may not result in death, be life-threatening, or require hospitalization may be considered a serious adverse effect when, based upon appropriate medical judgment, they may jeopardize the subject or subject and may require medical or surgical intervention to prevent one of the outcomes listed in this definition.

9.4. **Reporting of Serious Adverse Events**

The Investigator is required to report all SAEs that occur during the time period specified in Section 9.2. Once the Investigator becomes aware of an SAE, he/she must report the SAE to Medical Monitor within 24 hours.

The Medical Monitor may request additional supporting documentation as it becomes available, such as lab reports, electrocardiogram [ECG] reports, discharge summary, hospital notes, etc., if applicable. Additional follow-up information as it becomes available must be reported to the Medical Monitor.

The Investigator is also responsible for reporting all SAEs to the appropriate Institutional Review Board (IRB) in accordance with local laws and regulations. The Investigator is responsible for maintaining documentation in the study file that indicates the IRB has been properly notified.

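### A serious event caused by a procedure at the screening visit has no stated route to the Medical Monitor, because SAE reporting opens only at the first treatment visit

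*Protocol*

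**What the plan says.** - **Reporting window (Protocol 9.2).** "Report initiation for all AEs and SAEs will begin at the time of the first treatment visit"; it runs to the end of the final study visit.
- **SAE duty (Protocol 9.4).** "The Investigator is required to report all SAEs that occur during the time period specified in Section 9.2". The 24-hour report to the Medical Monitor belongs to this duty. A separate paragraph makes the investigator responsible for reporting all SAEs to the IRB under local rules and restates no window.
- **Events before dosing (Protocol 7.4).** "Events that emerge prior to first dose of study medication on Day 1 will be recorded in the medical history and not as AEs". There is no exception for serious or procedure-related events.
- **Start of procedures (Protocol 4 and 4.1.1).** V1 falls no more than 7 days before V2. "Screening assessments will commence at Visit 1 (V1) after obtaining signed informed consent".
- **Causality (Protocol 9.2.3).** Relationship is graded against study treatment only.
- **Screen failures (Protocol 11.2).** Their CRF is confined to the screen-failure page.
- **TEAEs (SAP 8.3.1).** Onset on or after the first treatment.

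**The concern.** Subjects accept the risk of protocol-required procedures from consent onward, but the sponsor's SAE reporting starts one visit later. If a procedure at V1 led to a hospitalisation, no visible rule obliges the site to tell the Medical Monitor. For a subject who goes on to treatment, the event would at least be noted as medical history. For a subject who fails screening, perhaps because of that event, the plan names no adverse event record at all.

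What is at stake is subject protection and the sponsor's ability to notice that a study procedure is causing harm. The randomised comparison is not at stake, since everything here happens before the first dose.

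**Working it through.** No formula applies, and the plan gives no figure to reproduce. The check is to read the sections against each other.

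**1. Which events fall outside the window?**

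| When the event occurs | Protocol 9.2 and 9.4 | Protocol 7.4 |
|---|---|---|
| V1 up to V2 | Outside the window; no Medical Monitor duty | Medical history, not an AE |
| V2, before the infusion | Inside the window; reportable | Medical history, not an AE |
| From the first dose | Inside the window; reportable | Does not apply |

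The first row is the gap. The second is a contradiction between sections.

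**2. How long is the gap, and what happens in it?** The interval from V1 to V2 is at most 7 days, and screening is a single visit. Procedures at V2 fall inside the 9.2 window, which opens at that visit. The scheduled procedures left outside are therefore those of V1 alone. The plan randomises 80 subjects, so the gap applies to at least 80 V1 visits plus one for each screen failure. The number of screen failures is not given.

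**3. Is there an exertion test at V1?** This has to be inferred, in four steps.
- The 6MWT is analysed as change from baseline (Protocol 2.2.2), and baseline is the last value before the first randomised treatment (SAP 7.1). A walk test must therefore take place before dosing, at V1 or V2.
- Protocol 7.6 gives the visits that combine a 6MWT with dosing as "i.e., Visit 6, 12, and 18". V2 is a dosing visit ("Visit 2 (Day 0) defined as day of first Ampligen") and is not among them.
- In Protocol Tables 4-1 and 4-2, the only row whose marks at dosing visits are exactly V6, V12 and V18 is also marked at V1 and V26. Its label is blacked out.
- V12 is in week 6 and V26 is labelled week 13, which are the two 6MWT endpoint weeks.

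If the list in 7.6 is complete, the baseline walk is done at V1. The gap does not depend on this, because 4.1.1 already places procedures at V1.

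**4. Does the visible text close the gap elsewhere?** Sections 9.1 to 9.4 read as continuous text, so the missing provision does not look like an effect of redaction. The investigator's screening log (Protocol 13.1) records the reason for ineligibility, but it is kept at the site and is not a report to the Medical Monitor.

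**5. The V2 mismatch.** Section 9.2 opens at the visit and 7.4 cuts at the dose. Section 9.1 sides with 7.4 for abnormal examination and laboratory findings, which count as AEs only after treatment has started. In addition, the first dose falls on Day 1 in 7.4 but on Day 0 in 4.2.1.

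**The case against.** The strongest objection is that the event may still be reported. A reader might infer from 9.2 and 7.4 that a serious screening event would reach nobody. The documents do not support that. The IRB paragraph in 9.4 covers all SAEs and repeats no time limit. One can reply that 7.4 stops a pre-dose event from being an AE, and so from being an SAE under 9.3. But the basic AE definition in 9.1 has no start time, so that reply is an interpretation. What stands is that the IRB might be told, voluntary reporting is not barred, and the Medical Monitor is still not covered by any explicit rule.

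A second tempting reading is that 7 days of procedures go unmonitored. They do not: 7 days is the longest interval, and the procedures are those of one visit.

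Third, the walk test at V1 should not be taken as established. The V1 procedure list and the row labels are blacked out, and the text of Protocol 7.16 on the 6MWT is not in the public copy. The SAP calls the test sub-maximal, 7.6 provides for vital signs around it where clinically indicated, and Protocol 3.1 requires a crash cart at sites. The documents give no reason to expect a serious event at V1.

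Finally, the start point is a stated choice, and nothing in these documents is breached by it. That is fair, and it keeps the point at the level of an improvement.

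**Conclusion.** The point holds in limited form and is a cheap improvement. Taken together, 9.2, 9.4 and 7.4 leave a serious event caused by a V1 procedure without a stated route to the Medical Monitor, and screen failures are the least covered. The extent is one scheduled visit per consented subject, followed by an interval of at most 7 days. Such events should be few, but the documents give no rate.

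This rests on the visible text of Section 9 being complete. The likely presence of the 6MWT at V1 adds some weight but is not needed. Efficacy results do not change. Neither do TEAE results, because TEAEs are defined by onset on or after first treatment. The disagreement between 7.4 and 9.2 at V2 is real, but it covers only the time at that visit before the infusion.

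**What to change.** - In Protocol 9.2, start reporting of SAEs related to protocol-required procedures at signed consent, so that the 24-hour duty in 9.4 covers them. Make the matching exception in 7.4.
- Add a relatedness-to-procedure item beside the treatment causality scale in 9.2.3. Without it, sites cannot say which pre-dose events qualify.
- In 11.2, allow the SAE form to be completed for screen failures.
- In the SAP, list these events separately and leave the TEAE definition in 8.3.1 as it is.
- Reconcile 7.4 with 9.2 for events at V2 before dosing, and use one day number for the first dose.

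The cost is a few sentences of protocol wording, one added causality item, a CRF permission for screen failures and one short listing. The downside is a few extra reports.

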9.2.1. Impact on Study Treatment

The impact the event had on the study treatment will be assessed as either: dose increased, dose not changed, dose rate reduced, dose reduced, drug interrupted, drug withdrawn, not applicable, or unknown. The "not applicable" assessment will be used only when the subject is no longer in the Treatment Phase of the protocol.

9.2.2. CTCAE Grade (Intensity) Assessment

The guidelines outlined in CTCAE v5.0 will be used for assessing the intensity of the event. The general guidelines for assessing the AE grade appear below. Full guidelines may be obtained at http://evs.nci.nih.gov/ftp1/CTCAE.

Grade	Description
Grade 1	Mild; asymptomatic or mild symptoms; clinical or diagnostic observations only; intervention not indicated.
Grade 2	Moderate; minimal, local, or noninvasive intervention indicated; limiting age- appropriate instrumental activities of daily living (ADL)*.
Grade 3	Severe or medically significant but not immediately life-threatening; hospitalization or prolongation of hospitalization indicated; disabling; limiting self-care ADL [†] .
Grade 4	Life-threatening consequences; urgent intervention indicated.
Grade 5	Death related to AE.

Table 9-1: CTCAE v5.0 General Guidelines

*Instrumental ADL refers to preparing meals, shopping for groceries or clothes, using the telephone, managing money, etc. †Self-care ADL refer to bathing, dressing and undressing, feeding self, using the toilet, taking medications, and not bedridden. -Common Terminology Criteria for Adverse Events (CTCAE), v5.0: November 27, 2017

9.2.3. Causality Assessment

AEs will be assigned a relationship (causality) to the study treatment. The Investigator will be responsible for determining the relationship between an AE and the study treatment. The type of event, organ system affected, and timing of onset of the event will be factors in assessing the likelihood that an AE is related to the study treatment. Relationship of AEs to study treatment will be classified as follows:

- 1. Definitely related: This category applies to those AEs that the Investigator feels are incontrovertibly related to the study treatment. An AE may be assigned an attribution of definitely related if or when it meets all of the following criteria: (1) it follows a reasonable temporal sequence from administration of the study treatment; (2) it could not be reasonably explained by the known characteristics of the subject's clinical state, environmental or toxic factors, or other modes of therapy administered to the subject; (3) it follows a known response pattern to treatment with the study treatment.
- 2. Probably related: This category applies to those AEs which, after careful medical consideration at the time they are evaluated, are felt with a high degree of certainty to be related to the study treatment. An AE may be considered probable if or when (must have three): (1) it follows a reasonable temporal sequence from administration of the study treatment. (2) It could not readily have been produced by subject's clinical state, environmental or toxic factors, or other therapies administered to the subject. (3) Disappears or is decreased upon discontinuation of the study treatment. (4) It follows a known response pattern to treatment with the study treatment.
- **3. Possibly related**: This category applies to those AEs which, after careful medical consideration at the time they are evaluated, are judged unlikely but cannot be ruled out with certainty to the study treatment. An AE may be considered possible if or when (must have two): (1) it follows a reasonable temporal sequence from administration of the study treatment. (2) It could not

readily have been produced by subject's clinical state, environmental or toxic factors, or other therapies administered to the subject. (3) Disappears or is decreased upon discontinuation of the study treatment. (4) It follows a known response pattern to treatment with the study treatment.

- 4. Unlikely related: In general, this category can be considered applicable to those AEs which, after careful medical consideration at the time they are evaluated, are judged likely to be unrelated to the study treatment. An AE may be considered unlikely if or when (must have two): (1) it does not follow a reasonable temporal sequence from administration of the study treatment. (2) It could not readily have been produced by subject's clinical state, environmental or toxic factors, or other therapies administered to the subject. (3) Disappears or is decreased upon discontinuation of the study treatment. (4) It does not follow a known response pattern to treatment with the study treatment.
- **5.** Unrelated: This category applies to those AEs which, after careful consideration at the time they are evaluated, are clearly and incontrovertibly due to extraneous causes (disease, environment, etc.) and determined with certainty to have no relationship to the study treatment.

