2.2.4. Safety Outcome Measures

- Incidence of treatment-related adverse events.
- Incidence and severity of treatment-emergent adverse events (TEAEs).
- Incidence of serious adverse events (SAEs).
- Incidence of TEAEs and SAEs leading to discontinuation of study medication.
- Changes in blood chemistry, hematology, and coagulation parameter results.
- Changes in vital signs including temperature, pulse, respiratory rate, systolic and diastolic blood pressure.
- Changes in physical examination results.
- Change in electrocardiogram (ECG) results.

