8.3.1 Adverse Events

Adverse events will be classified by system organ class (SOC) and preferred term (PT) according to the most recent version of MedDRA dictionary.

TEAE are defined as adverse events with onset date on or after the first treatment. TEAEs will be summarized by treatment group, System Organ Class, and preferred term. The following TEAE summaries will be provided:

- a) Overall (*i.e.*, regardless of severity or relationship to treatment)
- b) Adverse events by severity
- c) Related adverse events by severity
- d) Adverse events leading to treatment discontinuation by severity

e) Adverse events leading to death by severity

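### Protocol 9.2.3: the Possibly related and Unlikely related categories overlap in wording and in most criterion patterns, so treatment-related AE coding is poorly reproducible

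*Protocol*

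**What the plan says.** Protocol 9.2.3 asks the investigator to place each AE in one of five causality categories. Categories 1 to 4 combine a governing sentence with a list of criteria; category 5 has a governing sentence only.

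- Category 3, Possibly related, covers events that "are judged unlikely but cannot be ruled out with certainty to the study treatment". Its rule begins "An AE may be considered possible if or when (must have two" and is followed by four criteria, the first being that "it follows a reasonable temporal sequence from administration of the study treatment".
- Category 4, Unlikely related, covers events that "are judged likely to be unrelated to the study treatment". Its rule begins "An AE may be considered unlikely if or when (must have two" and is also followed by four criteria.
- Category 5, Unrelated, requires that the event be "determined with certainty to have no relationship to the study treatment".

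The split feeds a listed outcome. Protocol 2.2.4 opens its safety outcomes with "Incidence of treatment-related adverse events", and SAP 8.3.1 plans a summary headed "Related adverse events by severity". The visible text does not say which of the five categories count as related.

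**The concern.** The governing sentences of categories 3 and 4 describe the same belief: the drug probably did not cause the event. The qualifier in category 3 about not excluding the drug with certainty does not help, because category 4 does not claim certainty either; only category 5 does. The category 3 sentence also lacks a word that would make it read grammatically, which suggests a drafting slip.

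The criteria lists might have settled the matter, but category 4 is not the mirror image of category 3. Timing and known response pattern are reversed. Absence of a ready alternative cause, and improvement on stopping the drug, appear in the same form in both lists. Evidence that points towards the drug therefore counts towards Unlikely.

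The coding is done by each investigator, at up to 10 centers (Protocol 3.1). If Possibly counts as related and Unlikely does not, the same event can be inside or outside the first-listed safety outcome depending on who codes it.

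**Working it through.** The plan states no figure on this point, so there is none to reproduce. The check is an enumeration of the printed rules.

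**Inputs (Protocol 9.2.3).** Let T = reasonable temporal sequence, A = no ready alternative cause, D = disappears or decreases on stopping, P = known response pattern. Each is 1 if met and 0 if not, giving 2⁴ = 16 patterns.

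- Definite: T, A and P all met (its alternative-cause wording differs slightly and is treated as A).
- Probable: T + A + D + P ≥ 3.
- Possible: T + A + D + P ≥ 2.
- Unlikely: U = (1 − T) + A + D + (1 − P) ≥ 2, because criteria 1 and 4 are reversed and criteria 2 and 3 are not.

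A criterion that cannot be assessed is counted as not met.

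**Step 1: the six patterns with exactly two criteria met.** These are Possible but neither Probable nor Definite.

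| Met | U | Also Unlikely (U ≥ 2)? |
|---|---|---|
| T, A | 0+1+0+1 = 2 | yes |
| T, D | 0+0+1+1 = 2 | yes |
| T, P | 0+0+0+0 = 0 | no |
| A, D | 1+1+1+1 = 4 | yes |
| A, P | 1+1+0+0 = 2 | yes |
| D, P | 1+0+1+0 = 2 | yes |

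Five of six fit both categories.

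**Step 2: the five patterns with three or four criteria met.** U is 3 for T, A, D; 3 for A, D, P; 2 for all four; and 1 for T, A, P and for T, D, P. Three of the five therefore meet Probable and also Unlikely. An event meeting all four criteria fits Definite, Probable, Possible and Unlikely together.

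**Step 3: the five patterns with one or no criterion met.** U is 2 for none, 3 for A alone and 3 for D alone; these are Unlikely only. U is 1 for T alone and for P alone; these fit neither list.

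**Totals.** Possible: 6 + 5 = 11. Unlikely: 5 + 3 + 3 = 11. Both: 5 + 3 = 8. Neither: 2.

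**Step 4: the other reading of the rule.** If two means exactly two, the A, D pattern (U = 4) drops out of Unlikely, and 4 of the 6 patterns in Step 1 still fit both.

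**Step 5: would negating criteria 2 and 3 of category 4 be enough?** No. With all four criteria reversed and a minimum of two kept, any event with exactly two causal criteria also has two negated ones, so all 6 such patterns would still meet both lists. This describes a hypothetical list, not the printed one.

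**The case against.** **The boundary is not absent.** A reader might infer from the governing sentences that nothing separates the two categories. The lists do not support that. One pattern below Probable (T and P only) is Possible alone, three patterns are Unlikely alone, and the category names themselves imply an order. The boundary is blurred.

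**The scale may be meant to nest.** Every Probable event also meets Possible, so overlapping minima are built in, and an investigator may naturally assign the highest category met. That would settle the overlap between the lists. However, 9.2.3 does not state this order, both rules are permissive, and the governing sentence of category 3 would still direct an event thought unlikely to Possibly. The objection stands as a plausible practice, not as a rule in the document.

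**The cut for related is not shown.** The visible text does not place it between categories 3 and 4. If only Definite and Probable counted, the category 3 wording would not change the count, although the Probable and Unlikely overlap in Step 2 would remain. Some text around the safety analyses and planned tables has been removed, so the missing mapping cannot be called an omission.

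**Dilution of the drug-placebo contrast cannot be sized.** A reader might infer a definite loss. If a fraction f of subjects without a truly related event had an unlikely event filed as related, equally in both arms, the difference would become (p₁ + (1 − p₁)f) − (p₀ + (1 − p₀)f) = (p₁ − p₀)(1 − f). The algebra is correct, but the documents give neither the rates nor f, so no figure is claimed.

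**The consequence is limited.** SAP 8.3 plans descriptive safety analysis only, SAP 8.3.1 also tabulates TEAEs whatever their relationship to treatment, and investigators are blinded (Protocol 8.5). All of this stands and bounds the importance of the point.

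**Conclusion.** Categories 3 and 4 overlap in their governing sentences and in their criteria. On the printed rules, 8 of 16 patterns meet both, and 5 of the 6 that are Possible but not Probable or Definite also meet Unlikely (4 of 6 on the exactly-two reading). These are counts of patterns, not shares of the AEs that will occur; the documents give no basis for weighting them.

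The same event can be coded either way, so the descriptive summary of treatment-related AEs is poorly reproducible between investigators, on the condition that Possibly counts as related. Efficacy analyses and the all-causality TEAE table are not affected. The point is an internal inconsistency in an operative classification rule: worth correcting because it feeds a listed safety outcome, but not a threat to the trial's main comparison.

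**What to change.** 1. Reconcile categories 3 and 4 in Protocol 9.2.3. Reword the governing sentence of category 3, for example: a causal relationship is a reasonable possibility.
2. Use the same four causal criteria throughout and make the counts exclusive: probably or definitely = three or more; possibly = exactly two; unlikely = at most one. This replaces the un-negated criteria 2 and 3 of category 4. The 16 patterns then split 5 / 6 / 5 with no overlap between these groups and no pattern left out (three or more: 4 + 1 = 5; exactly two: 6; at most one: 4 + 1 = 5). Category 5 stays apart through its certainty requirement.
3. Confirm in SAP 8.3.1 which categories count as related, if removed text does not already say so.

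The cost is a wording change in the protocol and the eCRF guidance, at most one SAP sentence, and possibly a blinded re-check of AEs already coded as possibly or unlikely related.

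### The Unlikely related checklist in Protocol 9.2.3 reverses only two of its four criteria, so an event meeting all four causal criteria passes it

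*Protocol*

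**What the plan says.** Protocol 9.2.3 sets five causality categories and leaves the grade to the Investigator: "The Investigator will be responsible for determining the relationship between an AE and the study treatment". Each category opens with an overall judgement, and categories 1 to 4 add a checklist.

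- **Definitely** needs all three of: temporal sequence, no other reasonable explanation, known response pattern.
- **Probably** needs three of four: (1) temporal sequence, (2) no ready alternative cause, (3) improvement on stopping, (4) known response pattern.
- **Possibly** uses the same four criteria with a lower bar: "An AE may be considered possible if or when (must have two". Its opening judgement covers events "judged unlikely but cannot be ruled out with certainty to the study treatment".
- **Unlikely** is for events that "are judged likely to be unrelated to the study treatment". It also needs two of four. The first two are "1) it does not follow a reasonable temporal sequence from administration of the study treatment. (2) It could not readily have been produced by" other causes, and the last two are "3) Disappears or is decreased upon discontinuation of the study treatment. (4) It does not follow a known response pattern to treatment" with the study drug.
- **Unrelated** has no checklist and applies only where the event is "determined with certainty to have no relationship to the study treatment".

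The incidence of treatment-related AEs is a listed safety outcome (Protocol 2.2.4, SAP 2.6.4). SAP 8.3.1(c) tabulates related AEs by severity. The visible text does not say which of the five categories count as related.

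**The concern.** Having no ready alternative cause, and improving when treatment stops, support a drug effect in the Probably and Possibly lists. In the Unlikely list the same two statements, unreversed, support the opposite conclusion. That contradicts the category's own opening judgement. The sentence is complete in the text, so neither redaction nor PDF reading explains it.

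Two outputs rest on this grading, and the effect could go either way depending on what counts as related:

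- If Unlikely counts as not related, a strongly causal event graded Unlikely lowers the count. An event with only a temporal link, graded Possibly because no checklist fits, raises it.
- If Unlikely counts as related, moves between Possibly and Unlikely change nothing. A temporal-only event pushed to Unrelated lowers the count.

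**Working it through.** **Inputs.** The four criteria and the required numbers come from Protocol 9.2.3. The plan gives no figure to reproduce. Code each causal criterion 1 (met) or 0 (not met): T temporal sequence, N no ready alternative cause, D improves off treatment, K known response pattern. This gives 2^4 = 16 patterns.

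**Rules.**

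- Definitely: T, N and K all 1. Its second criterion is worded differently and is treated as N, which is an assumption.
- Probably: T + N + D + K ≥ 3.
- Possibly: T + N + D + K ≥ 2.
- Unlikely as written: (1−T) + N + D + (1−K) ≥ 2.
- Unlikely with all four items reversed: (1−T) + (1−N) + (1−D) + (1−K) ≥ 2.

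The opening judgement of each category is not modelled.

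**Key case.** With T = N = D = K = 1, the written Unlikely score is 0 + 1 + 1 + 0 = 2. It passes whether the requirement means at least two or exactly two. The same event scores 3 of 3 for Definitely and 4 of 4 for Probably. With all items reversed its Unlikely score is 0.

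**Opposite case.** With T = K = 1 and N = D = 0 (a ready alternative cause and no improvement on stopping), the written Unlikely score is 0. The two facts that argue against the drug earn nothing.

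**All 16 patterns: number passing Unlikely**

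| Causal criteria met | Patterns | As written | All four reversed |
|---|---|---|---|
| 0 | 1 | 1 | 1 |
| 1 | 4 | 2 | 4 |
| 2 | 6 | 5 | 6 |
| 3 | 4 | 2 | 0 |
| 4 | 1 | 1 | 0 |
| Total | 16 | 11 | 11 |

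- **Wrongly admitted:** TND, NDK and TNDK pass Unlikely as written (2 + 1 = 3), and all three also pass Probably. After reversal: 0.
- **No checklist fits:** T only and K only each meet one Possibly criterion and one Unlikely criterion. Unrelated is open to them only with certainty. That is 2 patterns as written and 0 after reversal.
- **Status changes:** TND, NDK and TNDK leave Unlikely; T, K and TK enter. That is 3 + 3 = 6 of 16.

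**Treatment not stopped.** If D cannot be judged, 8 patterns of T, N and K remain. As written, TN and NK meet both Possibly and Unlikely, and T and K meet neither (2 and 2). After reversal: 0 and 0.

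**A separate boundary matter.** Possibly and Unlikely each need two of four, so they overlap at exactly two causal criteria: 5 patterns as written (TN, TD, ND, NK, DK) and 6 after reversal (TK joins). The missing reversal does not cause this overlap. The opening judgements do not separate the two categories cleanly either, because Possibly also describes its events as judged unlikely.

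**The case against.** The best defence is that the checklist does not decide the grade. The Investigator does, and must first judge the event likely to be unrelated. An event meeting every causal criterion would rarely be judged so, and it also satisfies Definitely, Probably and Possibly. Each route to a wrong count needs someone to go against explicit text: the opening judgement of Unlikely, the two-criteria requirement of Possibly, or the certainty required for Unrelated. Patterns are not equally frequent, so counting them does not measure harm. Grading is blinded (Protocol 8.5), safety output is descriptive (SAP 8.3), and the all-TEAE table and SAE reporting (Protocol 9.4) do not depend on causality.

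Most of this stands, and it limits the size of the point. It does not remove the contradiction. If two criteria are read as necessary but not sufficient, an event with only a temporal link still cannot be graded Unlikely or Possibly, and judgement alone does not open a category for it. With up to 10 centers (Protocol 3.1), sites may resolve the conflict differently. It is also fair that the Possibly/Unlikely overlap is a separate matter, and that any tie-break for it is optional.

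**Conclusion.** The error is real and is visible on the face of Protocol 9.2.3: items (2) and (3) of Unlikely related point the wrong way for that category. As written, 3 of 16 patterns with strong causal support pass the checklist and 2 of 16 fit none; reversing the two items clears both. These counts rest on treating each criterion as a yes/no item, on reading the requirement as at least two, and on leaving the opening judgements aside.

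The effect on reported safety results is not quantifiable. Neither the frequency of such events nor the categories counted as related can be seen, and nothing in the documents suggests one arm would be affected more. Severity is minor. Confidence is high for the wording error; actual misgrading is possible but not shown.

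**What to change.** In category 4 of Protocol 9.2.3, reverse item (2) so that it is met when the event could readily be explained by the subject's condition, environment or other therapies. Reverse item (3) so that it is met when the event does not resolve or lessen after treatment stops, and mark it not applicable if treatment was not stopped. Keep the two-of-four requirement.

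Separately and optionally, clarify the boundary between categories 3 and 4, for example by grading as Possibly any event that meets both checklists. After the reversal this would leave 5 patterns fitting only Unlikely and send 6 to Possibly, so it could raise the related count if Possibly counts as related and Unlikely does not. Add no precedence rule among categories 1 to 3, where the Investigator's judgement should continue to decide.

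The cost is a short amendment with IRB approval (Protocol 11.3) and a note to sites. Before unblinding, blinded investigators would re-check AEs graded Unlikely, and those graded Possibly or Unrelated that may have fitted no checklist. No new data are needed.
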